**Table 1: Testing Schedule**

Screening	Pre-Treatment	Post Treatment #	One-Month f/u#
D-KEFs Color-Word Interference Test		D-KEFs Color-Word Interference Test	D-KEFs Color-Word Interference Test
NART	*BRIEF-A	*BRIEF-A	*BRIEF-A
TOMM	PSQI	PSQI	PSQI
	Tower of London	Tower of London	Tower of London
EXAMINER	EXAMINER	EXAMINER	EXAMINER
PCL-M	RBANS	RBANS	RBANS
	Stop-Signal Task	Stop-Signal Task	Stop-Signal Task
	Beck Depression Inventory-II	Beck Depression Inventory-II	Beck Depression Inventory-II
	CRIS	CRIS	CRIS

\*patient and family or friend

Description of Measures

## Screening Measures

Color-Word Interference Test or the Flanker Task will be used to determine an objective deficit in inhibition by a score of  $\geq 1.5$  standard deviations (SD) below the normative mean. The Delis-Kaplan Executive Function System (D-KEFS) was designed to detect executive dysfunction believed to be mediated by the frontal lobes. Since it is generally believed that soldiers, diagnosed with mTBI and PTSD due to blast injury, have damage to the frontal lobes, the Color-Word Interference Test of the D-KEFS will be used to screen for subjects that have deficits in inhibition. The D-KEFS Tower Test, which is a version of the TOL, loads onto the same factor (Inhibition) as the Color-Word Interference Test (Latzman, 2010). Therefore, a deficit of  $\geq 1.5$  SD on the DKEFS Color-Word Interference Test would negate possible ceiling effects on the primary outcome measure. The test retest of the Color-Word Interference Test is suitable with a range of .49 to .86 for ages 20-49. The validity was "reasonable" for detecting patients with frontal lobe lesions from normal patients (Homack, 2005).

## EXAMINER

A battery of 10 executive function tasks have developed by a NINDS funded project to use in clinical research studies. The tasks take approximately 60 minutes to administer via a computer and result in 12 primary variables. Tasks include: Dot counting (count blue dots on a series of screens and recall the number of dots across screens), N-back (identify whether a series of locations match the location presented 1 or 2 before), Flanker (indicate the direction of an arrow that is flanked by arrows pointing in the opposite direction), Continuous Performance Test (respond to certain stimuli and withhold response to other stimuli on a computer screen), Anti-saccades (move eyes toward a stimulus and moves eyes away from a stimulus), Set-shifting (switch between a homogeneous matching task and a heterogeneous matching task), Phonemic Fluency (name as many words as possible with the same letter), Category Fluency (name as many items as possible in a category), Unstructured Task (complete puzzles within 6 minutes with the goal of earning as many points as possible), and the Social Norms Questionnaire (answer yes no questions about socially appropriate behaviors). Test re-test reliability is .94 and correlated with the FrsBe -0.57 in a multi-neurologic population. Patients that score at least 1.5 SD below the mean on the Flanker task will be included in the study. Secondary analysis will be conducted to determine the effect size on each of the EXAMINER tasks.

National Adult Reading Test (NART) is an oral reading test consisting of 50 words (Nelson and Willison, 1991). The NART can be used to estimate premorbid intelligence and will be used as a screen. Similar to Levine et al. (2007), we will use the cut off score of  $> 90$  as an inclusion criterion to ensure that frontal lobe impairment is not the result of low premorbid intelligence, and that the subject will be able to read the material during treatment.

Test of Memory Malingering (TOMM): is frequently used to detect poor effort on neuropsychological assessment and has been validated with TBI patients (Tombaugh, 1996; Slick et al., 2004; DeBoar, 2007). This test will be used to screen out patients scoring 45 or below on Trial 2 or the Retention Trial (Trial 1 scores will not be used) to provide a level of confidence to the results of outcome measures.

Primary Outcome Measure: Tower of London (TOL): is a computerized program in which patients are shown two pictures simultaneously of a goal board and a test board (Unterrainer et al, 2006). Each picture shows three balls of different colors arranged on three pegs, with the balls in a unique arrangement in each picture. Patients are instructed to determine the fewest possible moves of the balls in the test picture to make the

arrangement of balls identical to that of the goal picture within 60 seconds. The screen reports whether the response is correct or incorrect. Test administration is less than 45 minutes for each session (pre/post/follow-up). Each set consists of 70 problems of variable difficulty, determined by variables, such as, the number of moves needed to solve the problem (Berg and Byrd, 2002). In turn, each set consists of the same number of 4, 5, 6 or 7 move problems and has the same average difficulty level. Difficulty rating is based on global and specific problem parameters shown to affect the planning process (Kaller, 2007, 2008, 2009; Berg, Byrd, McNamara, & Case, 2010; Kaller, Unterrainer, Rahm, & Halsband, 2004). The dependent variables are the total time spent solving the problem and the optimal moves made toward the goal display.

Based on our previous studies, executive function represents three factors (behavior regulation, emotional regulation and metacognition) (Waid, Wen, Heaton, andVELOZO, submitted to Neuropsychology). GMT is a metacognitive training with emphasis on planning prior to engaging in a complex task. Therefore, a primary measure that captures the planning and problem solving of a multi-step task, called the Tower of London (TOL), was selected. Based on results from our preliminary study, the dependent variables of total time and optimal moves will be used to determine treatment effect. While, not all of the participants in our previous work demonstrated significant improvement on these variables, group differences based on paired T-tests were significant in Total Time ( $p=0.026$ ) and Optimal Moves ( $p=0.022$ ) from baseline to treatment. In addition to our findings, Levine (2011) demonstrated a significant change in the TOL following GMT for a mixed neurological sample compared to a control group. Thus, the TOL appears to be sensitive to the effects of GMT.

#### Stop Signal Task

An "X" or "O" stimuli is presented visually on a computer screen. Participants are asked to press the left button for an "X" and to press the right button for an "O" as quickly and as accurately as they can. If the stimuli are followed by an auditory tone (stop signal) they are asked to not press the button. Dependent measures are Response Time on Go Trials (RT) and Stop Signal Response Time (SSRT). Three sessions lasting approximately 10 minutes each will be conducted. Stop Signal will be used as a secondary outcome measure to determine the effect size.

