### **Aim 1.**

#### **Aim 1 is to test the benefits of GMT for improving executive function.**

Hypothesis 1a: GMT will significantly improve problem solving ability compared to the control group (primary measure: time to completion on the Tower of London (cTOL). Since PTSD is prevalent and a potentially influencing co-morbidity, we will investigate whether there is a significant interaction between treatment group and PTSD severity.

Secondary measures include number of optimal moves on the TOL; and measures derived from the Stop Signal Task (SST; a measure of inhibition control).

Exploratory Hypothesis 1.a. GMT will significantly improve everyday activities that require executive function skills (primary measure: Behavior Rating Inventory of Executive Function-Adult version, secondary measure: CRIS).

**Analysis Plan for Hypothesis 1. and Hypothesis 1.a.** To test the first specific aim (hypothesis 1), the primary analysis will use two sample t-test to compare group A (intervention) and group B (control) on improvements in time to completion on the TOL. In addition, as an exploratory analysis, we will perform a regression analysis that includes treatment group, PTSD severity and their interaction as independent variables, to adjust for PTSD severity and to investigate whether there is interaction between treatment group and PTSD severity. Similar analyses will be performed for hypothesis 1 for secondary outcome variables of change in index of optimal moves on the TOL and reaction time (RT) and accuracy on SST. To test hypothesis 1a, exploratory *tertiary analysis* using paired t-tests will determine whether treatment effect generalizes to executive function performance in everyday activities (BRIEF-A) or engagement in community participation (CRIS).

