### **Aim 1.**

**Aim 1 is to test the benefits of GMT for improving executive function.**

Hypothesis 1a: GMT and home practice device will significantly improve problem solving ability compared to the control group (primary measure: time to completion on the Tower of London (cTOL). Since PTSD is prevalent and a potentially influencing co-morbidity, we will investigate whether there is a significant interaction between treatment group and PTSD severity. Secondary measures include number of optimal moves on the TOL; and measures derived from the Stop Signal Task (SST; a measure of inhibition control).

Exploratory Hypothesis 1.b. GMT and functional practice will significantly improve everyday activities that require executive function skills (primary measure: Behavior Rating Inventory of Executive Function-Adult version, secondary measure: CRIS).

**Analysis Plan for Hypothesis 1.a. and Hypothesis 1.b.** To test the first specific aim (hypothesis 1a), the primary analysis will use two sample t-test to compare group A (intervention) and group B (control) on improvements in time to completion on the TOL. In addition, as an exploratory analysis, we will perform a regression analysis that includes treatment group, PTSD severity and their interaction as independent variables, to adjust for PTSD severity and to investigate whether there is interaction between treatment group and PTSD severity. Similar analyses will be performed for hypothesis 1 for secondary outcome variables of changes in index of optimal moves on the TOL and reaction time (RT) and accuracy on SST. To test hypothesis 1b, exploratory *tertiary analysis* using paired t-tests will determine whether treatment effect generalizes to executive function performance in everyday activities (BRIEF-A) or engagement in community participation (CRIS).

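### The Stop Signal Task is described by go-trial RT and SSRT, but both Aim 1 analysis plans name RT and an undefined accuracy score, so SSRT is missing from the named secondary analysis

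*Combined protocol and SAP*

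**What the plan says.** Three places in the combined protocol and SAP bear on the Stop Signal Task (SST) as an outcome.

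- **Measure description (section 6, Stop Signal Task).** Participants make a left or right button press to a visual stimulus, "as quickly and as accurately as they can". On some trials a tone follows: "If the stimuli are followed by an auditory tone (stop signal) they are asked to not press the button". The outcomes are then listed: "Dependent measures are Response Time on Go Trials (RT) and Stop Signal Response Time (SSRT"). The role of the task is also given: "Stop Signal will be used as a secondary outcome measure to determine the effect size".
- **Hypothesis 1a (sections 5 and 7, Aim 1).** The secondary measures include "measures derived from the Stop Signal Task (SST; a measure of inhibition control").
- **Aim 1 analysis plans.** After the primary two-sample t-test and the exploratory regression on PTSD severity, similar analyses are planned for further variables. Section 5 lists "secondary outcome variables of change in index of optimal moves on the TOL and reaction time (RT) and accuracy on SST". Section 7 lists "secondary outcome variables of changes in index of optimal moves on the TOL and reaction time (RT) and accuracy on SST".

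SSRT appears nowhere outside the measure description. For this task, accuracy appears there only as an instruction to the participant, not as a scored variable.

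**The concern.** The measure description and the analysis plans do not name the same variables, and the difference falls on the part of the task that matters most. The SST is in the trial because it measures inhibition control. Go-trial RT comes from trials on which nothing has to be stopped, so by itself it cannot show that inhibition changed. SSRT is the listed measure that relates to stopping, and it is the one left out of the analysis text.

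Accuracy does not reliably fill the gap, because the task has two kinds of correct behaviour: pressing the correct button on a go trial, and withholding the press after the tone. The plan does not say which is scored, or whether they are combined. An analyst who follows the Aim 1 text literally could therefore report two SST results of which neither concerns stopping. With three candidate variables and no rule, the choice of which to report could also be made after the results are seen.

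**Working it through.** No figure in the plan needs to be reproduced: the documents give no effect size, standard deviation or error rate for any SST variable. The check is a comparison of the texts.

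**Step 1. List the variables by source.**

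| Variable | Section 6, Stop Signal Task | Section 5, Aim 1 analysis plan | Section 7, Aim 1 analysis plan |
|---|---|---|---|
| Go-trial RT | listed | named, as RT | named, as RT |
| SSRT | listed | not named | not named |
| Accuracy | not listed | named | named |

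**Step 2. Count the overlap.** Described = {RT, SSRT}. Analysed = {RT, accuracy}. The union has 3 members and the intersection has 1 (RT). One variable is listed but not analysed, and one is analysed but not listed.

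**Step 3. Could RT in the analysis text include SSRT?** No. The measure description attaches the abbreviation RT to go trials and gives SSRT its own label. The analysis plans use the same abbreviation, RT.

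**Step 4. How many of the 2 analysed SST variables reflect stopping?** Go RT does not. Accuracy depends on its meaning:

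- correct presses on go trials only: 0 of 2;
- successful stops only: 1 of 2;
- a mixture of both: at most 1 of 2, and that one is diluted by go performance.

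**Step 5. Is it an isolated slip?** The same pair, RT and accuracy, appears in both section 5 and section 7. One typing error in one section does not explain it, although text carried from one section to the other might.

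**Step 6. What does the repair add?** The Aim 1 secondary list has 3 variables: optimal moves, SST RT and SST accuracy. Adding SSRT gives 3 + 1 = 4. Replacing accuracy with SSRT gives 3 - 1 + 1 = 3. This counts accuracy as a single tested variable; if go accuracy and stopping success were both formally tested, the count would be one higher again.

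**The case against.** The strongest reply is that this is a labelling inconsistency and that no outcome is lost. The document is a combined protocol and SAP. Its measure description lists SSRT as a dependent measure and says that the task serves to determine an effect size, and Hypothesis 1a refers in general terms to measures derived from the task. Read together, SSRT is planned, and two summary sentences leave it out. Much of this stands. A reader might infer that SSRT has been dropped from the trial or that no SSRT effect size could be reported; the documents do not support that. What remains is that the analysis text goes on from the general phrase to say which variables are tested, and SSRT is not among them.

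A second reply is that SSRT is no better specified than accuracy: it is named, but no scoring method is given. That is correct, and the repair has to cover it.

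A third is that the documents do not rank the SST variables. RT is the one named in all three places, so nothing in the text justifies demoting it. That also stands, and the repair keeps go RT as an analysed variable.

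A reader might further infer that the gap damages the sizing of a later randomized trial, which the Abstract gives as a goal. No section ties that sizing to the SST, and the named primary measure is Tower of London time to completion, so that inference is not supported.

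**Conclusion.** The inconsistency is real and should be corrected before group data are examined. Of the three SST variables mentioned, one is common to the description and the analysis plans. SSRT is missing from the named secondary analysis, and accuracy is in it without a definition. Depending on what accuracy means, none or at most one of the two analysed SST variables reflects stopping.

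The scope is limited. It concerns one secondary outcome, and the primary Tower of London comparison is untouched. SSRT remains in the trial as a listed measure.

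The conclusion rests on two readings: that the variables listed in the Aim 1 analysis plans are the ones to be tested, and that SSRT, as its name implies, is the listed measure specific to stopping. The second is taken from the label and the task description, since the plan gives no formula for it.

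**What to change.** - **Sections 5 and 7, Aim 1 analysis plans.** Add between-group change in SSRT to the analysed SST variables, alongside go RT. Report its effect size with a confidence interval, which matches the role that section 6 gives the task.
- **Section 6, Stop Signal Task.** State how SSRT is computed.
- **Accuracy.** Either define it in section 6 by trial type, with go accuracy and stopping success kept separate, or remove it from both analysis plans. If it is kept, say which of the two is formally tested and report the other descriptively.

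The cost is wording in three places. No extra testing is needed: the task description already provides that "Three sessions lasting approximately 10 minutes each will be conducted", and Table 1 schedules the task before treatment, after treatment and at the one-month follow-up. The statistical downside is at most one more secondary comparison, provided no more than one accuracy score is tested, and none if SSRT takes the place of accuracy.

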#### Measures for Secondary Analysis

Beck Depression Inventory (BDI): is a 21-item questionnaire filled out by the individual diagnosed with TBI in the presence of the Principal Investigator. Questions are rated using a 4-point scale and cover symptoms of depression such as hopelessness, irritability, guilt, fatigue, weight loss and lack of interest in sex. The reliability of the BDI in TBI has been reported at .92 (Green, 2001; Beck et al, 1996).

Post-Traumatic Stress Disorder (PTSD) symptom checklist-military (PCL-M): The checklist is a 17-item self-report measure of the 17 DSM-IV symptoms of PTSD with a 5-point rating scale ranging from rarely to extremely frequent. The range of total score is 17 to 85. Internal consistency for the overall scale is .95 with cross validation to clinician-administered interviews ranging from .64 for Vietnam veterans to .83 for motor vehicle accident and assault victims (Weathers, 1991 & 1993; Blanchard et al, 1996). The PCL-M will be used to determine the impact of PTSD on the response to treatment.

Pittsburgh Sleep Quality Index (PSQI): is a 19-item self-rated questionnaire for evaluating subjective sleep quality over the previous month. Seven component scores are added to obtain a global score ranging from 0–21, with higher scores indicating worse sleep quality. The PSQI has a sensitivity of 89.6% and specificity of 86.5% for identifying cases with sleep disorder and has been used in a wide range of population-based and clinical studies. Since sleep disturbances are common complaints for Veterans returning from deployment and has been known to impair cognition, the PSQI will be used to determine whether sleep disturbances interfere with treatment response.

Repeatable Battery for the Assessment of Neuropsychological Status (RBANS): is a cognitive screening instrument The RBANS is composed of 12 subtests that yield 5 index scores and a total score. The subtests of List Learning and Story Memory comprise the Immediate Memory Index; Figure Copy and Line Orientation yield the Visuospatial/Constructional Index; Picture Naming and Semantic Fluency yield the Language Index; and Digit Span and Coding comprise the Attention Index. Four subtests make up the Delayed Memory Index, specifically, List Recall, List Recognition, Story Recall, and Figure Recall (Randolph, Tierney, Mohr, & Chase, 1998). Administration is approximately 20 minutes and has been used to assess cognition in mTBI (Cooper et al., 2010). The index scores of the RBANS will be used to characterize the patient's cognitive capacity and to determine whether particular aspects of cognitive ability impact response to treatment.

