### **Aim 2**

Aim 2 is to investigate factors which affect response to treatment.

Hypothesis 2. Baseline cognitive ability, depression, sleep, and presence of PTSD will have a significant effect on response to treatment.

Analysis Plan for Hypotheses 2. To test the second specific aim, a general linear regression will be used to determine whether any of the four factors is associated with response to treatment. The analysis will be restricted to the participants assigned to the intervention group. The dependent variable for the regression model will be 'time to completion' on the TOL, and the independent variables will be CWI, BDI-II, PCL-M and PSQI scores.

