- Diagnosis of Mild TBI or concussion by a physician or neuropsychologist in the medical record compliant with the American Congress of Rehabilitation Medicine; any of three following criteria are met: 1) loss of consciousness less than 30 minutes with a Glasgow Coma Scale of 13 or above; 2) any loss of memory for events immediately before and after the event (not longer than 24 hours); any alteration of mental state at the time of accident; 3) any focal neurological deficits that may, or may not, be transient (ACRM, 1993).
- Executive dysfunction determined by at least 1.5 standard deviation below the average scaled score (corrected for age) on either the Delis-Kaplan Executive function System (D-Kefs) Color Word Interference Test, or the EXAMINER flanker task.
- Age 18 to 55 years
- At least 4 months post injury
- Family member or friend that is willing to provide feedback

Exclusion Criteria:

- History of pre-morbid learning disability
- History of psychiatric diagnosis sufficiently severe to have resulted in inpatient hospitalization.
- Neurological disease unrelated to TBI (seizure disorder, stroke, ADHD)
- Score < 90 on National Adult Reading Test (NART)
- Failure of validity testing on either the Test of Memory Malinger (TOMM),. Score of 45 or less on TOMM Trial 2 or retention trial.
- Reported alcohol or substance abuse within the past year
- Reported involvement in current litigation
- Recent change of medications for seizures, depression or memory.
- Currently enrolled in other cognitive therapy that cannot be discontinued
- Does not speak English fluently
- Not competent to provide consent (also, not able to demonstrate understanding of expectations of study and potential risks of participation).

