## **Aim 2**

Aim 2 is to investigate factors which affect response to treatment.

Hypothesis 2a. Baseline cognitive ability, depression, sleep, and presence of PTSD will have a significant effect on response to treatment.

**Analysis Plan for Hypotheses 2a.** To test the second specific aim, a general linear regression will be used to determine whether any of the four factors is associated with response to treatment. The analysis will be restricted to the participants assigned to the intervention group. The dependent variable for the regression model will be 'time to completion' on the TOL, and the independent variables will be CWI, BDI-II, and PCL-M scores.

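### Neither Aim 2 model includes RBANS, the measure given the task of testing whether cognitive ability affects response; baseline cognitive ability is left to CWI, an inhibition screen and entry test

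*Combined protocol and SAP*

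**What the plan says.** Hypothesis 2 (section 5) and Hypothesis 2a (section 7) name four factors: "Baseline cognitive ability, depression, sleep, and presence of PTSD will have a significant effect on response to treatment". Both analyses are linear regressions within the intervention arm, but the predictor lists differ:

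- Section 5, Specific Aims, Aim 2: "the independent variables will be CWI, BDI-II, PCL-M and PSQI scores".
- Section 7, Statistical Methods, Aim 2: "the independent variables will be CWI, BDI-II, and PCL-M scores".

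RBANS is in neither list. Its entry under Measures for Secondary Analysis in section 6 states that "The RBANS is composed of 12 subtests that yield 5 index scores and a total score". It gives the index scores two jobs: to describe cognitive capacity and "to determine whether particular aspects of cognitive ability impact response to treatment". Table 1 (Testing Schedule) lists RBANS at pre-treatment, post-treatment and follow-up.

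CWI is not spelled out in the Aim 2 text; it is read here as the D-KEFS Color-Word Interference Test. The Screening Measures text says that "the Color-Word Interference Test of the D-KEFS will be used to screen for subjects that have deficits in inhibition". The inclusion criteria require a score at least 1.5 SD below average "on either the Delis-Kaplan Executive function System (D-Kefs) Color Word Interference Test, or the EXAMINER flanker task". Table 1 lists the test at screening, with no pre-treatment entry.

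**The concern.** The plan names a cognitive battery for a question, schedules it before treatment, and then writes the models for that question without it. The cognitive part of Hypothesis 2 falls to a score that the protocol describes in terms of inhibition, and that also helped decide who could enrol.

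Two things are at stake. A finding that cognitive ability does or does not affect response would really be a finding about performance on one inhibition task. And because no RBANS analysis is specified, the choice of RBANS score (a total or any of five indices) and of model remains open until after the results are seen.

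**Working it through.** **1. Match factors to predictors.**

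| Factor in Hypothesis 2 | Section 5 model | Section 7 model |
|---|---|---|
| Depression | BDI-II | BDI-II |
| PTSD | PCL-M | PCL-M |
| Sleep | PSQI | none |
| Baseline cognitive ability | CWI, by elimination | CWI, by elimination |

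The documents never say that CWI stands for cognitive ability. No other candidate is in either model.

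**2. Look for RBANS elsewhere.** The Aim 1 analyses use the Tower of London, Stop Signal Task, BRIEF-A and CRIS. The EXAMINER entry announces a secondary effect-size analysis. No analysis is stated for RBANS beyond the sentence in its own entry. The gap is textual and needs no assumption.

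**3. What the entry rule could do to CWI.** The documents give neither the CWI-Flanker correlation nor the source distribution, so both are assumed. CWI and Flanker are simulated as bivariate normal with unit SD, and a person enrols if either is at or below -1.5.

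| Assumed source correlation | Enrolled correlation, source mean 0 | Enrolled correlation, source mean -1 SD |
|---|---|---|
| 0.2 | -0.56 | -0.31 |
| 0.5 | -0.36 | -0.04 |
| 0.7 | -0.11 | +0.23 |

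For correlations of 0.2 to 0.5, about 32% to 47% enter on Flanker alone, and the CWI SD among enrollees is about 0.81 to 1.09 of the source SD.

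**4. How well CWI then reflects its own true score.** Use the protocol's retest range, r = .49 to .86.

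- Only those below the CWI cut-off, source mean 0: the truncated variance is v = 0.150 (SD 0.39), and the squared correlation is r·v/(r·v + 1 - r). For r = .86: 0.129/(0.129 + 0.14) = .48. For r = .49: 0.0735/(0.0735 + 0.51) = .13.
- All enrollees, which is the group Aim 2 draws on (simulated, source correlation 0.2 to 0.5, CWI error independent of Flanker): about .78 to .87 for r = .86, and about .11 to .44 for r = .49.

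The second line is the relevant one. The loss is small at the upper reliability and can be large at the lower.

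**5. Cost of adding RBANS.** The planned intervention arm is 38 (38/54 = 70.4%), before the exclusions in section 7. The documents give no alpha or power for Aim 2, so two-sided 0.05 and 80% are assumed. Residual df = n - p - 1, partial R² = f²/(1 + f²), and f² is solved from the noncentral F with noncentrality n·f².

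- Section 5 model, 4 predictors: df = 38 - 4 - 1 = 33; f² = 0.219; detectable partial R² = 0.219/1.219 = 0.18 for one coefficient.
- With the RBANS total added, 5 predictors: df = 32; f² = 0.220; partial R² = 0.220/1.220 = 0.18.
- Five indices in place of CWI, 8 predictors: df = 29; a joint 5-df test of the indices needs f² = 0.407, so partial R² = 0.407/1.407 = 0.29.

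One total score is nearly free. Five indices tested as a block are not.

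**The case against.** The other side has several sound points.

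- **A separate RBANS analysis may be intended.** RBANS sits under measures for secondary analysis and also serves to describe the sample, so it would be too strong to say that it has no use. But no separate analysis is specified, so the gap stands.
- **CWI is not severely truncated.** A reader might infer this from the entry criterion, or from the .48 and .13 above. Those two figures hold only for people who qualified on CWI. Aim 2 also includes those who qualified on Flanker, and their presence restores much of the spread.
- **A null or reversed CWI coefficient need not be an artefact of selection.** A reader might infer that too. Selecting on a predictor does not by itself bias its slope in a correctly specified linear regression. Bias through the entry rule requires Flanker to predict response independently of CWI while being left out of the model. Nothing in the documents establishes that.
- **CWI does not merely mark the entry route.** Route explains about 59% to 68% of CWI variance in the simulations, but splitting any normal variable at its median gives 2/π = 64%. CWI keeps graded information within each route.
- **Screening CWI is a valid baseline value.** It precedes treatment, so its timing is no defect.
- **RBANS is not shown to be the better instrument.** The documents give no reliability for it, it may be subject to incidental selection if it correlates with either entry test, and its indices do not include inhibition. This is a reason to keep CWI beside RBANS. It does not justify leaving out the measure that the protocol itself assigned to the question.

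**Conclusion.** The point holds as an inconsistency between the stated role of RBANS and both Aim 2 models. Followed as written, the plan would answer the cognitive part of Hypothesis 2 with a narrow inhibition score that is also an entry test. This rests on the text, on reading CWI as Color-Word Interference, and on assigning it to cognitive ability by elimination. Section 4 names the Stop Signal Task, not Flanker, as the second screening test; CWI is one of the two in either version.

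The effect of the entry rule is a possible further weakness of unknown size. The enrolled CWI-Flanker correlation runs from about -0.56 to +0.23 across assumed source correlations of 0.2 to 0.7 and means of 0 to -1 SD, so the documents support neither its sign nor its magnitude. Aim 2 is a secondary aim, and the primary two-sample t-test on Tower of London time does not depend on it.

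**What to change.** - In the Aim 2 models of sections 5 and 7, add the pre-treatment RBANS total score as the single pre-specified term for baseline cognitive ability.
- Keep CWI in both models, labelled as a separate inhibition covariate.
- Examine the five RBANS index scores one at a time and label them exploratory. If each is tested at 0.05 and the tests are treated as independent, the chance of at least one false positive is 1 - 0.95^5 = 23%, so the report should say that these results are unadjusted.
- Amend the RBANS entry in section 6 to name the total as the main term and the indices as exploratory, so that all three places agree.

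While the lists are being aligned, the sponsor should also settle whether PSQI belongs in the section 7 model, which refers to four factors but has no predictor for sleep. That is a separate point.

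The cost is SAP and protocol wording and one model degree of freedom among about 38 treated participants (fewer after the section 7 exclusions). Detectable partial R² stays at about 0.18 under the assumed alpha and power. No new data are needed, because RBANS is already scheduled.
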